5.2.1 Legislation and guidelines used for preparation

The present clinical trial will be conducted in accordance with the published principles of the guidelines for Good Clinical Practice (ICH-GCP). These principles cover, amongst other aspects, ethics committee procedures, the obtaining of informed consent from trial subjects, adherence to the trial protocol, administrative documentation, data collection, trial subjects' medical records (source documents), documentation and reporting of complications related to the implementation of the KDIGO guidelines, preparation for inspections and audits, and the archiving of trial documentation. All investigators and other staff directly concerned with the study will be informed that domestic and foreign supervisory bodies, the competent federal authorities and authorised representatives of the responsible institution have the right to review trial documentation and the trial subjects' medical records at any time.

5.3 Registration

Before the trial is started, it will be registered under Current Controlled Trials (www.controlled-trials.com) or another trial register approved by the World Health Organisation (WHO) (http://www.who.int/ictrp/en/).

5.4 Data protection

The provisions of data protection legislation will be observed. It is assured by the responsible institution that all investigational materials and data will be pseudo-anonymised in accordance with the data protection legislation before scientific processing.

Trial subjects will be informed that their pseudo-anonymised data will be passed on in accordance with provisions for documentation and notification pursuant to § 12 and § 13 of the GCP Regulations to the recipients described there. Subjects who do not agree that the information may be passed on in this way will not be enrolled into the trial.

Laboratory data will be maintained in a separate, secure location with access limited only to laboratory personnel.

CONFIDENTIAL

Date: 16.02.2017 Version: V1

6 Statistics

6.1 Endpoints

The primary endpoint of this trial is the compliance rate, i.e. the proportion of patients who have been treated according to the trial protocol(KDIGO recommendations fulfilled at all time).

Secondary endpoints include occurrence of AKI within 72 hours after cardiac surgery, moderate and severe AKI, severity of AKI, renal recovery at days 30,60 and 90, 30-day, 60-day and 90-day mortality, length of ICU stay, length of hospital stay, need and duration of RRT, RRT at days 30, 60 and 90, MAKE₃₀, MAKE₆₀ and MAKE₉₀ (major adverse kidney events consisting of mortality, dialysis dependency persistent renal dysfunction (defined as serum creatinine \geq 2x compared to baseline value).

The randomization ratio is 1:1.

6.2 Sample size

The required sample size is n=280 patients in total. This sample size is determined as follows.

Patients will be randomized in a 1:1 ratio to one of the two treatment arms (intervention versus control). Randomization serves to estimate the incidence of AKI as secondary outcome to generate pre-information in terms of a pilot study for an upcoming confirmatory trial.

The primary endpoint of the PrevAKI-multicenter trial is the compliance rate, i.e. the proportion of patients who have been treated according to the trial protocol (KDIGO recommendations fulfilled at all time). In order to estimate the compliance rate, the two treatment groups will be pooled together. In the primary analysis the compliance rate across all study patients will be estimated along with a two-sided 95% confidence interval (CI).

As the compliance rate cannot be quantified in advance, we pursue a worst case approach and assume a compliance rate of 50%. In this case the CI has maximal width. Based on this assumption, with a sample size of n=280 patients the calculated 95% CI according to Clopper-Pearson (Fleiss 2003) ranges from 44% to 56%. Therefore, in case of any observed compliance rate apart from the worst-case scenario, the 95% CI is never wider than 56%-44%=12%. This corresponds to an estimation of the compliance rate with a precision of plus/minus 6%.

CONFIDENTIAL

Date: 16.02.2017 Version: V1

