	Severity of AKI (according to the KDIGO guidelines)					
	 Renal recovery at days 30, 60 and 90 (renal recovery is defined as serum creatinine levels < 0.5 mg/dl higher than baseline serum creatinine) 					
	30-day, 60-day and 90-day mortality					
	Length of ICU stay					
	Length of hospital stay					
	Need and duration of renal replacement therapy					
	• RRT at days 30, 60, 90					
	 MAKE₃₀, MAKE₆₀ and MAKE₉₀ (major adverse kidney events consisting of mortality, dialysis dependency, persistent renal dysfunction (defined as serum creatinine ≥ 2x compared to baseline value) 					
	Determination of different biomarkers					
	 Assessment of safety: complications in particular those related to the implementation of the KDIGO guidelines will be 					
	documented. No side effects have been reported.					
Number of subjects	To be assessed for eligibility: n=1000					
	To be allocated to the trial: n=310					
	To be analyzed: n=280 (140/ treatment arm)					
Time plan	First patient first visit (FPFV): 01/06/2017					
	Last patients first visit (LPFV): 31/05/2018					
	Last patient last visit (LPLV): 01/08/2018					
	Final study report: 01/11/2018					
	7 mai stady roport. 01/11/2010					

CONFIDENTIAL

Date: 16.02.2017 Version: V1

Statistics	Power analysis
	The required sample size is n=280 patients in total. This sample size is
	determined as follows:
	Patients will be randomized in a 1:1 ratio to one of the two treatment
	arms (intervention versus control). Randomization serves to estimate the
	incidence of AKI as secondary outcome to generate pre-information in
	terms of a pilot study for an upcoming confirmatory trial.
	The primary endpoint of the PrevAKI-multicenter trial is the compliance
	rate (Primary outcome: KDIGO recommendations fulfilled at all time), i.e.
	the proportion of patients who are treated according to the trial protocol.
	In order to estimate the compliance rate, the two treatment groups will
	be pooled together. In the primary analysis the compliance rate across
	all study patients will be estimated along with a two-sided 95%
	confidence interval (CI).
	As the compliance rate cannot be quantified in advance, we pursue a
	worst case approach and assume a compliance rate of 50%. In this case
	the CI has maximal width. Based on this assumption, with a sample size
	of n=280 patients the calculated 95% CI according to Clopper-Pearson
	(Fleiss 2003) ranges from 44% to 56%. Therefore, in case of any

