2.4 Benefit-risk assessment

Patients included in the trial have an increased risk for the development of AKI.

In the validation group, the bundle of supportive measures recommended by the KDIGO guidelines will be implemented, whereas patients in the control group receive standard of care therapy. Cardiacoutput (e.g. measured by echocardiography; at initiation and then every 3h up to 12h) will be measured in both groups without informing the treating physician about the values. The intervention may reduce the occurrence and severity of AKI.

The KDIGO guidelines include optimization of volume status and hemodynamic parameters, discontinuation of nephrotoxic agents when possible, discontinuation of ACEi and ARBs, close monitoring of serum creatinine and urinary output, and avoidance of hyperglycemia. To this date, the benefit of these simple and uncomplicated measures has not been proven. Patients assigned to the control group will not have any disadvantages compared to non-participation in the study.

All the patients included in this trial receive standard therapy according to the current clinical routine at each center. The patient's primary physicians will determine the remainder of patient management consistent with established best practice within the institution.

Significance

The occurrence of AKI after cardiac surgery is associated with an increased risk of morbidity and mortality. The KDIGO guidelines recommend to implement various measures in high risk patients to prevent AKI. However, it has not been proven whether the implementation of these measures reduces the occurrence of AKI after cardiac surgery. Patients at high risk for AKI will be identified by using the AKI biomarkers [TIMP-2]*[IGFBP7] which will be measured 4h after cardiac surgery.

Given the fact that more than 2 million patients are scheduled for cardiac surgery each year worldwide, reducing the occurrence of AKI by biomarker-guided implementation of the KDIGO guidelines would result in a remarkable positive effect for many patients, health care systems and health economics.

To plan a large randomized outcome study, in which we investigate whether biomarker-guided implementation of the KDIGO guidelines can reduce the occurrence of AKI after cardiac surgery, we have to know the adherence to the trial protocol. Once we have these data, we can perform the power analysis for the outcome study.

CONFIDENTIAL

3 Organizational and administrative aspects of the trial

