4.6.2 Control intervention

Patients in the control group will receive standard of care. In these patients, cardiac output will also be measured (e.g. via echocardiography; at initiation and then every 3h up to 12h) but the treating physician will not be informed about the values.

(07-Anlt-16) 16.02.2017 Version: V1

Date:

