4.7 Efficacy and safety variables

4.7.1 Measurement of efficacy and safety variables

- 4.7.1.1 Primary target variable
 - Compliance rate (proportion of patients who are treated according to the trial protocol):
 KDIGO recommendations fulfilled at all time
- 4.7.1.2 Secondaryand other target variables
- Occurrence of AKI within the first 72 hours after cardiac surgery (AKI will be defined according to the KDIGO guidelines)
- Moderate and severe AKI within 72 hrs (according to the KDIGO guidelines)
- Severity of AKI within 72 hrs
- Renal recovery

Renal recovery at hospital discharge and at days 30, 60 and 90 will be defined asserum creatinine levels < 0.5 mg/dl higher than baseline.

- 30-day, 60.day and 90-day mortality
- Length of stay in intensive care unit and hospital

CONFIDENTIAL

Date: 16.02.2017 Version: V1

Information on ICU and hospital stays will be documented. From admission to ICU admission until follow-up (by phone) at day 90, the location of the patient within the hospital will be documented in the CRF. The following will be recorded for each patient

- Date and time of admission to ICU
- Date and time of discharge from ICU
- Date and time of discharge from hospital
- Need and duration of RRT during hospital stay
- RRT at days 30, 60 and 90
- MAKE₃₀, MAKE₆₀ and MAKE₉₀ (major adverse kidney events consisting of mortality, dialysis dependency persistent renal dysfunction (defined as serum creatinine ≥ 2x compared to baseline value)
- Determination of different biomarkers

Blood and urine samples for biomarkers will be collected at the time of randomization and 12 hrs later

 Assessment of complications related to the implementation of the KDIGO guidelines will be documented.

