6.3 Statistical analysis plan

The trial is designed to examine the feasibility of the trial protocol in a multicenter setting (as previously described).

The **descriptive analysis** of the data will include the calculation of means, standard deviations, and absolute and relative frequencies of the baseline and follow-up data. Randomization will be checked by suitable two-sided statistical tests (Chi-Square, or Fisher's exact test for categorical data, Students' t-Test or Mann-Whitney-U tests for continuous data). If normality of the data is not given non-parametric methods will be used.

In the primary statistical analysis the compliance rate across all recruited study patients will be estimated along with a two-sided 95% confidence interval (CI)according to Clopper-Pearson (Fleiss 2003).

Secondary endpoints will be analyzed in the ITT collective using Fisher's exact tests or chisquared tests for categorical data, and Student's t-tests or Mann-Whitney-U tests for continuous data. Prognostic risk factors for AKI will be identified using a multivariable logistic regression analysis, accounting for confounding factors. In particular, based on a full model with potentially relevant covariates (e.g. sex, age, previous heart surgery, preoperative creatinine) the final model will be established applying a stepwise variable selection procedure.

7 Use of trial findings

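### The primary compliance rate pools the KDIGO arm with a standard-of-care arm, so it identifies neither bundle delivery nor control-arm uptake

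*Combined protocol and SAP*

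**What the plan says.** Section 6.2 defines the primary endpoint as "the proportion of patients who have been treated according to the trial protocol (KDIGO recommendations fulfilled at all time". The same specification, "KDIGO recommendations fulfilled at all time", appears in the synopsis, section 1, section 4.7.1.1 and section 6.1.

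Section 6.2, like the synopsis, then says: "In order to estimate the compliance rate, the two treatment groups will be pooled together". Section 6.3 confirms that this is the operative analysis: "In the primary statistical analysis the compliance rate across all recruited study patients will be estimated", with a two-sided Clopper-Pearson 95% interval. The sample size rests on that pooled interval at an assumed rate of 50%, and the precision is given as plus/minus 6%. The synopsis plans 310 patients allocated and 280 analysed, 140 per arm.

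The bundle is assigned to the intervention arm only (the validation group; sections 4.2, 4.6 and 4.6.1). For the other arm, section 4.6.2 says: "Patients in the control group will receive standard of care". Cardiac output is also measured in controls, at initiation and every 3 h up to 12 h, and is withheld from the treating physician. The plan does not say what makes a control patient compliant. Neither 6.1 nor 6.3 lists compliance by arm.

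Section 2.4 gives the purpose. Adherence must be known in order to plan the larger trial: "Once we have these data, we can perform the power analysis for the outcome study".

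**The concern.** The endpoint definition and the pooling rule do not fit together. The definition asks whether a KDIGO bundle was fulfilled, but half the patients in the denominator are not assigned that bundle.

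The definition also carries two descriptions of compliance, treatment per protocol and KDIGO fulfilment. These coincide in the intervention arm and diverge in the control arm. The plan does not say which governs for controls.

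What is at stake is the use of the result. Planning a two-arm outcome trial needs two figures: how often the bundle was delivered where it was assigned, and how often it was received where it was not. The gap between them determines how far a treatment effect is diluted. One pooled percentage gives neither, and the stated precision belongs to the pooled percentage.

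**Working it through.** **Inputs from the documents.** 280 analysed, 140 per arm, 310 allocated 1:1 (synopsis); assumed rate 50%, exact two-sided 95% CI, both arms pooled (6.2, 6.3). Arm-specific rates are not given, so every arm rate below is an assumption for illustration.

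**1. The plan's own figure.** Clopper-Pearson limits for x of n are Beta(0.025; x, n−x+1) and Beta(0.975; x+1, n−x). For 140/280 they are 43.99% and 56.01%, a width of 12.02 points and a half-width of 6.01. This is the largest width over all x at n=280. The stated 44% to 56% reproduces, so the arithmetic is sound. The issue is what is being estimated.

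**2. The pooled rate.** With equal arms, pooled rate = (pI + pC)/2, where pI and pC are the proportions scored compliant in the intervention and control arms.

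*Reading A: KDIGO fulfilment is scored in both arms.*

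| Assumed pI | Assumed pC | Compliant / 280 | Pooled rate (95% CI) |
|---|---|---|---|
| 100% | 0% | 140 + 0 = 140 | 50% (44.0–56.0) |
| 95% | 5% | 133 + 7 = 140 | 50% (44.0–56.0) |
| 70% | 30% | 98 + 42 = 140 | 50% (44.0–56.0) |
| 50% | 50% | 70 + 70 = 140 | 50% (44.0–56.0) |
| 90% | 5% | 126 + 7 = 133 | 47.5% (41.5–53.5) |

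The first row is perfect delivery with full separation. The fourth is no separation at all. Both give the same headline. With no control uptake the pooled rate cannot exceed 50%.

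*Reading B: each arm is scored against its own assignment.* Here pC is the rate at which control-arm duties were met.

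| Assumed pI | Assumed pC | Compliant / 280 | Pooled rate (95% CI) |
|---|---|---|---|
| 50% | 100% | 70 + 140 = 210 | 75% (69.5–80.0) |
| 90% | 60% | 126 + 84 = 210 | 75% (69.5–80.0) |
| 90% | 100% | 126 + 140 = 266 | 95% (91.8–97.2) |

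Bundle delivery of 50% and of 90% can give the same pooled 75%, depending on how well the control measurements were done.

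**3. Precision where the bundle is assigned.** Worst case, same exact method:

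- 140 analysed: 70/140 gives 41.44% to 58.56%, half-width 8.6 points.
- All randomised to the arm, 310/2 = 155: 77/155 gives 41.56% to 57.81%, half-width 8.1 points.
- Away from the worst case at n=140: 80% gives 72.4–86.3%, and 90% gives 83.8–94.4%.

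Keeping a full width of at most 12.0 points within the arm would take about 281 patients in it, or 562 in total at 1:1.

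**The case against.** The strongest defence starts from the stated objective, which is adherence to the trial protocol in a multinational setting (synopsis; 6.3 speaks of the protocol's feasibility). On that view, the share of all patients handled as assigned is a coherent, if coarse, answer. Controls do have duties that a site can miss: serial cardiac output measurements, done by independent research staff (4.2.2) and withheld from the treating physician. This stands as far as it goes. A reader might infer that controls would be compliant almost by definition under this reading, and the documents do not support that. But the defence needs a control-arm criterion, which the plan does not contain, and it still averages two different tasks.

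A second defence is that allocation is recorded, so compliance by arm can be tabulated from the same data. In addition, the intention-to-treat AKI rates by arm already reflect imperfect delivery and contamination. Both points are fair. They make this a gap in prespecification, not a loss of data. The headline and its stated precision would still be the pooled ones.

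A third is that section 2.4 does not say the pooled percentage will be entered in the next power analysis as intervention-arm adherence. That is also right. A reader might infer that a wrong adherence figure will be carried forward, but the text shows only that the prespecified figure is not the one needed.

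**Conclusion.** The point holds. As written, the primary analysis yields one rate from which neither intervention-arm delivery nor control-arm uptake can be recovered, under either reading of compliance. This follows from the pooling rule and equal allocation and does not depend on any assumed rate. The precision of plus/minus 6 points is right for 280 pooled patients. For the intervention arm it is about 8.6 points (140 analysed) or 8.1 points (about 155 randomised).

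The size and direction of any distortion are unknown, because the documents give no rates by arm. Two stronger readings should be resisted:

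- That a pooled 50% is compatible with any delivery rate from 0% to 100%. This is only an algebraic bound under reading A. Its lower end needs every control and no intervention patient to fulfil KDIGO. Under reading B with controls near 100%, a pooled 50% would force delivery to near zero.
- That the primary result says nothing about feasibility. Under reading B it says something about overall protocol adherence, but not about the bundle.

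**What to change.** - In the synopsis, 6.2 and 6.3, make the primary estimate the proportion of intervention-arm patients with the KDIGO recommendations fulfilled, with an exact 95% CI.
- Report the same score in the control arm and the between-arm difference, each with a 95% CI. If a pooled rate is kept, label it descriptive. If adherence to control-arm duties is of interest, define it and report it separately.
- State the denominator and match the precision to it: about plus/minus 8.6 points for 140 analysed, or about 8.1 points if all of about 155 randomised to the arm are counted, in place of 6.
- Write down how fulfilment is scored and over what period. Section 4.1.1 ends the intervention period at 12 h, while 4.6.1 attaches 48 h and 72 h to individual components. The scoring rule has to be reconciled with these.

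The cost is a change of wording and a less favourable stated precision. No extra patients are needed unless the sponsor wishes to keep plus/minus 6 points within the arm.

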6.3 Statistical analysis plan

The trial is designed to examine the feasibility of the trial protocol in a multicenter setting (as previously described).

The **descriptive analysis** of the data will include the calculation of means, standard deviations, and absolute and relative frequencies of the baseline and follow-up data. Randomization will be checked by suitable two-sided statistical tests (Chi-Square, or Fisher's exact test for categorical data, Students' t-Test or Mann-Whitney-U tests for continuous data). If normality of the data is not given non-parametric methods will be used.

In the primary statistical analysis the compliance rate across all recruited study patients will be estimated along with a two-sided 95% confidence interval (CI)according to Clopper-Pearson (Fleiss 2003).

Secondary endpoints will be analyzed in the ITT collective using Fisher's exact tests or chisquared tests for categorical data, and Student's t-tests or Mann-Whitney-U tests for continuous data. Prognostic risk factors for AKI will be identified using a multivariable logistic regression analysis, accounting for confounding factors. In particular, based on a full model with potentially relevant covariates (e.g. sex, age, previous heart surgery, preoperative creatinine) the final model will be established applying a stepwise variable selection procedure.

7 Use of trial findings

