4.2.1 Randomization

Prior to being randomized into the study, patients will have:

- Signed a written informed consent
- Completed screening
- Met all designated inclusion criteria and have no exclusion criteria

Randomization assignment (in a 1:1 ratio to the two treatment arms) will be given only to those patients fulfillingthe inclusion and none of the exclusion criteria and providing informed consent. Randomization will be performed by using a web-based randomization system. After identifying a high risk patient (urinary [TIMP2]*[IGFBP7] ≥ 0.3, NephroCheck® Test), patients will be assigned to control or intervention group, whereas the intervention will be provided by research staff not involved in the care of patient.

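### The AKI comparison that justifies randomising is planned without an effect measure or confidence interval, and AKI severity has no named ordinal analysis

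*Combined protocol and SAP*

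**What the plan says.** - **Purpose of randomising.** The primary endpoint, compliance, is estimated with both arms pooled and does not need randomisation. Section 6.2 gives the reason for it: "Randomization serves to estimate the incidence of AKI as secondary outcome to generate pre-information in terms of a pilot study".
- **Between-arm analysis.** Section 6.3 states "Secondary endpoints will be analyzed in the ITT collective" and then names Fisher's exact or chi-squared tests for categorical outcomes and t or Mann-Whitney tests for continuous ones. It gives no risk difference, risk ratio or odds ratio, no confidence interval and no significance level for these endpoints. The only interval in the plan is the Clopper-Pearson interval for pooled compliance.
- **Other relevant parts of section 6.3.** Descriptive analysis covers frequencies of follow-up data as well as baseline data. A multivariable logistic model for AKI offers sex, age, previous heart surgery and preoperative creatinine as example covariates. Its stated aim is to find prognostic factors, the final model is reached by stepwise selection, and neither treatment arm nor centre is named.
- **Severity.** Section 6.1 lists "moderate and severe AKI, severity of AKI, renal recovery at days 30,60 and 90" among the secondary endpoints. No section says which test applies to severity.
- **Allocation.** Section 4.2.1 says "Randomization will be performed by using a web-based randomization system". No stratification factor is stated.
- **Numbers.** The synopsis gives "To be allocated to the trial: n=310" and "To be analyzed: n=280 (140/ treatment arm").

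**The concern.** A pilot that randomises in order to inform a later trial has to deliver an estimate of the quantity of interest together with its uncertainty. The plan does this for compliance and sizes the trial on it. For AKI, the only outcome for which the arms need to be compared, it plans tests. A test result says whether the data are compatible with no effect. It does not say which effects remain plausible, and those determine the size of the confirmatory trial.

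Two smaller matters go with this. The trial is multinational, and sections 2.4 and 4.6 leave background care and the type of haemodynamic monitoring to each centre, so AKI risk may differ between centres; yet no centre term is planned. And KDIGO stage is ordered: if it is handled as categorical data under section 6.3, the ordering is lost.

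**Working it through.** **1. The plan's own figure.** The exact Clopper-Pearson interval for 140/280 is 43.99% to 56.01%, width 12.02 points, which is the maximum over all possible counts. This reproduces the 44% to 56% in section 6.2 and is not in dispute. No corresponding figure exists for AKI.

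**2. Inputs for AKI.** 140 per arm (synopsis). AKI 71.7% in control and 55.1% under intervention, from the earlier single-centre trial in section 2.2, used here as planning rates. The two-sided 5% level and the 90% power for the next trial are assumptions.

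**3. What an estimate would look like.**
- Incidence per arm, exact 95% CI: 100/140 gives 63.2% to 78.7%; 77/140 gives 46.4% to 63.4%.
- Risk difference: 0.717 − 0.551 = 0.166.
- SE = √(0.717×0.283/140 + 0.551×0.449/140) = √(0.45031/140) = 0.0567.
- 95% CI: 0.166 ± 1.96×0.0567 = 0.0548 to 0.2772.
- Risk ratio: 0.551/0.717 = 0.77. SE of the log = √(0.449/(140×0.551) + 0.283/(140×0.717)) = 0.093, giving 0.64 to 0.92.
- With all 310 allocated patients analysed (155 per arm), the half-width of the risk difference falls only from 11.1 to 10.6 points.

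**4. What that means for the next trial.** n per arm = (1.960 + 1.282)² × [p₁(1−p₁) + p₂(1−p₂)] / d², with p₁ = 0.717 and p₂ = p₁ − d. At the point estimate this is 10.507 × 0.45031 / 0.166² = 171.7.

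| Difference d | n per arm, formula above | n per arm, pooled variance under the null |
|---|---|---|
| 0.0548 (lower limit) | 1,491 | 1,494 |
| 0.166 (estimate) | 172 | 175 |
| 0.2772 (upper limit) | 61.5 | 65 |

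The range is 23- to 24-fold under either formula.

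**5. Severity.** The documents give no stage distribution, so three control-arm splits (none / stage 1 / 2 / 3) were assumed. The effect was a common odds ratio of (0.717/0.283)/(0.551/0.449) = 2.06, with 140 per arm and 20,000 simulated trials per split.

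| Assumed control split, % | Unordered chi-squared | Mann-Whitney on ordered stages |
|---|---|---|
| 28.3 / 35 / 25 / 11.7 | 80% | 91% |
| 28.3 / 45 / 20 / 6.7 | 79% | 90% |
| 28.3 / 25 / 28 / 18.7 | 81% | 91% |

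At an assumed odds ratio of 1.6, power is about 42% for chi-squared and 58% for the ordinal test.

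**6. Centre and creatinine.** The documents give neither the number of centres nor their heterogeneity. With 12 assumed centres of 12 patients per arm (10,000 simulated trials), power of the unstratified test versus the centre-stratified test is:
- no heterogeneity: 84% versus 83%;
- logit SD between centres 0.5: 81% versus 82%;
- logit SD 1.0: 72% versus 77%.

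A separate simulation adjusting for both centre and creatinine, with moderate to strong assumed effects, gave gains from 84% to 85% at the low end and from 73% to 80% at the high end.

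**The case against.** The strongest reply is that this is a feasibility trial. Its primary output is compliance with an exact interval, and section 2.4 ties the next trial's sizing to adherence: "Once we have these data, we can perform the power analysis for the outcome study" refers to adherence data. Section 6.2 speaks of estimating AKI incidence, not a treatment effect, and the descriptive frequencies supply that incidence as a point estimate. The interval and the contrast can be calculated by anyone from the counts. All this is correct, and it limits the damage: nothing is irrecoverable and the primary analysis is untouched. It does not remove the point. Estimation is the stated reason for randomising, and the plan prespecifies neither the effect measure nor its precision.

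Four stronger readings may tempt a reader, and the documents do not support them:
- **That the plan yields nothing on AKI except p-values.** The descriptive frequencies give proportions.
- **That baseline covariates are ignored.** The multivariable AKI model uses them. It falls short because its aim is prognostic, arm and centre are not named, and stepwise selection may drop terms; so it does not adjust the randomised comparison.
- **That the plan treats severity as unordered.** No test is assigned to it. The loss in step 5 arises only if stage is handled as categorical data.
- **That randomisation ignores centre.** Section 4.2.1 is silent on stratification; it does not rule it out.

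**Conclusion.** The point holds in limited form. For the randomised comparison, section 6.3 specifies only unadjusted tests, with no effect measure or interval for any secondary endpoint, while section 6.2 rests randomisation on estimation. The missing estimate with its interval is the main defect: if the single-centre rates recur, the AKI difference carries about ±11 points. That leaves the next trial's size undetermined between about 61-65 and about 1,490 per arm.

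The unnamed severity analysis could cost about 10 power points, conditional on the chi-squared reading and the assumed stage splits. The gain from adjusting for centre and creatinine runs from about nil to several power points. It depends on heterogeneity that the documents do not give, so it is a supporting argument only. This is an improvement worth making at almost no cost; it casts no doubt on the primary endpoint or on n = 280.

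**What to change.** In section 6.3:
- Report AKI incidence per arm with 95% CI, and the risk difference and risk ratio with 95% CI. Take the two effect measures from a prespecified model with treatment, preoperative creatinine and centre (for example, a logistic model with standardised risks), with no stepwise selection for the treatment effect. Keep the prognostic model as a separate analysis.
- Analyse KDIGO stage 0 to 3 by a proportional-odds model or a rank test, named in advance.

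In section 4.2.1, state whether randomisation is stratified. If the number of centres allows, stratify the web randomisation by centre with varying block sizes.

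The cost is some wording, slightly more analysis work and one setting in the randomisation system. Preoperative creatinine is already among the plan's candidate covariates and centre is known, so no new data are needed. If centres do not differ, the loss of power is negligible (84% to 83% in step 6). Sample size and primary endpoint stay as they are.
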